4. SUBJECT SELECTION AND WITHDRAWAL CRITERIA

4.1. Number of Subjects:

25 WAS/XLT Patients (10 of whom will have a blood draw only) + 10 Normal Control Patients = 35 Total Patients

4.2. Inclusion Criteria:

In order to be eligible for study entry, subjects must comply with the following:

- Males or females from 3 months to 80 years old
- Signed written informed consent obtained prior to study entry
- Clinical diagnosis of WAS or XLT
- Platelet levels less than $75 \times 10^9/L$
- Adequate renal and hepatic function (creatinine and bilirubin less than or equal to $1.5 \times ULN$, AST and ALT less than or equal to $2.5 \times ULN$)

4.3. Exclusion Criteria:

Any patient is ineligible for study entry if he/she:

- Over the age of 80
- Pregnant or lactating women
- Fertile men who are not practicing or who are unwilling to practice birth control while enrolled in the study or until at least 6 months after treatment

- Aspirin, aspirin-containing compounds, salicylates, non-steroidal anti-inflammatory medications (NSAIDS), clopidogrel or ticlopidine, warfarin or other vitamin K antagonists, unfractionated or low molecular heparin within 7 days of first treatment
- Red blood cell transfusion in the past four weeks
- Elevated ($> 1.5 \times$ ULN) prothrombin time (PT) or partial thromboplastin time (PTT)
- New York Heart Classification III or IV heart disease. Other severe cardiovascular or cardiopulmonary disease, including COPD.
- Known HIV infection, hepatitis B or C infection
- Any infection requiring antibiotic treatment within 3 days
- Other concurrent medical or psychiatric conditions that, in the Investigator's opinion, may be likely to confound study interpretation or prevent completion of study procedures and follow-up examinations.
- Prior malignancy with less than a 5-year disease-free interval, excluding nonmelanoma skin cancers and carcinoma in situ of the cervix

Eligibility criteria for controls:

- a) Within 5 years of the age of the enrolled patient
- b) No overt hematologic diagnosis
- c) Male

4.4. Withdrawal Criteria:

1. Treatment with eltrombopag should be discontinued because of abnormal liver tests if any of the following 4 conditions apply:

- ALT levels ≥ 3 times upper limit of normal (ULN) and bilirubin levels > 1.5 times ($> 35\%$ conjugated bilirubin) ULN,
- (2) ALT levels ≥ 3 times ULN and appearance or worsening of hepatitis symptoms or rash,
- (3) ALT levels remain ≥ 3 times ULN for ≥ 4 weeks, or

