6.2. Efficacy

Collection of platelet counts on week 1 (pre-dose), week 2, monthly during year 1, every two months during year 2, and every 3 months during years 3-6, along with platelet function studies. Bleeding symptoms will be monitored by bleeding score assessments.

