8.3. Data Analysis Considerations

Data from all subjects who receive eltrombopag will be summarized. Results will be summarized by visit. All displays should include the number of subjects with available data at that visit.

Study endpoints include bleeding score, platelet count, platelet function, megakaryopoiesis and platelet formation.

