8.3.1.1. Efficacy Analyses

Primary endpoint will be increasing platelet counts in WAS/XLT patients to above 50,000/ul. The generalizability of the data will depend upon including both WAS and XLT patients but no specific distribution of patients within these 2 groups is pre-specified. The proportion of patients showing this increase will be summarized with 95% confidence intervals. The proportion of patients maintaining this increase will be summarized for time points of interest.

Correlations will be evaluated graphically. In addition, Spearman rank correlation coefficients may be used to evaluate the association of platelet count and bleeding score, at each visit.

Any within-subject analyses may be based on Wilcoxon signed rank tests.

Secondary endpoints will involve reduction of bleeding in treated patients within 12 weeks, and to specifically examine the reduction in bleeding in those with platelet counts > 100,000/ul and also > 50,000/ul.

We anticipate that platelet function will improve as the platelet count increases but not normalize.

Therefore efficacy will depend on platelet counts, immature platelet fraction, platelet function by flow cytometry, and the bleeding score. Since the dose required may vary from patient to patient and may only be changed every 2 weeks, a platelet count > 50,000/ul at any time within the first 12 weeks will be considered a response. Similarly, secondary endpoints involving reduction in bleeding and improvement in platelet function will also be explored within a 4 to 12 week window for assessment.

Toxicity will depend upon adverse events, abnormal liver tests, and other abnormal findings.

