

SCHEDULE OF EVENTS
“Pathobiology of Thrombocytopenia and Bleeding in Patients with Wiskott-Aldrich Syndrome.” Protocol #: 0801009600

	Screening	Day 1/Baseline	Week 2	Week 4	Months ⁴ 2 – 12	Months ⁵ 14 - 24	Months ⁶ 27 - 72
Evaluation and Management							
Informed Consent	x						
Bleeding Score ¹	x	x	x	x	x	x	x
Standard of Care							
Physical Examination	x	x	x	x	x	x	x
Urinalysis	x						
Admission Panel (Includes liver tests such as ALT, AST, bilirubin)	x	x	x	x	x	x	x
CBC with Platelet and Diff	x	x	x	x	x	x	x
Diagnostic Tests for Platelet Function							
PT/PTT	x						
D-Dimers	x						
Fibrinogen	x						
PFA ²					x		
Immature Platelet Fraction (Platelet Reticulocyte Count) ³	x	x	x	x	x	x	x
Single Platelet Flow Cytometry ⁷	x			x	x ⁸		

1. The Page bleeding score will be administered at each visit in order to semi-quantitatively assess bleeding
2. PFA (Platelet function Analysis) will be assessed once for WAS/XLT patients and control patients at month 2, provided platelet count is >50 k
3. IPF will be obtained with each Cornell in-clinic CBC where possible
4. Subjects will have their blood drawn monthly and be seen every 3 months during the first year
5. Subjects will have their blood drawn every 2 months and be seen every 4 months in the second year
6. Subjects will have their blood drawn every 3 months and be seen every 6 months in the 3rd – 6th years
7. Single Platelet Flow Cytometry tests will be performed by [name] at screening, once between months 1-3, and once after 1-2 years on study.

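### The 12-week response rule in section 8.3.1.1 has no baseline term, so a patient who enters between 50,000 and 75,000/ul and does not change can be scored a responder

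*Combined protocol and SAP*

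**What the plan says.** Section 8.3.1.1 introduces the endpoint as "Primary endpoint will be increasing platelet counts in WAS/XLT patients to above 50,000/ul". It adds that "The proportion of patients showing this increase will be summarized with 95% confidence intervals" and that "The proportion of patients maintaining this increase will be summarized for time points of interest". Further down, after noting that doses differ between patients and change at most every two weeks, it gives the working rule: "a platelet count > 50,000/ul at any time within the first 12 weeks will be considered a response".

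Four other places bear on this:

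- **Section 4.2** sets the entry ceiling as "Platelet levels less than $75 \times 10^9/L", which is 75,000/ul.
- **Section 8.3** sets the analysis population: "Data from all subjects who receive eltrombopag will be summarized". Nothing excludes or separately classifies a patient by entry count.
- **Section 6.2** plans "Collection of platelet counts on week 1 (pre-dose), week 2, monthly during year 1", and the Schedule of Events has CBCs at Screening and at "Day 1/Baseline". A pre-dose count is therefore collected, but section 8.3.1.1 does not tie response to it.
- **Section 1.2** reports preliminary results with a baseline-linked criterion: at least one count of 50 x 10^9/L or more, and twice the baseline value. Section 8 does not carry this criterion forward.

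**The concern.** The entry ceiling lies above the response threshold. A patient can meet the working rule on the day of entry and needs only to stay there. Because section 6.2 labels the pre-dose count as week 1, even that count might be taken to qualify.

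There is no control arm, and section 3.1 says patients are compared with themselves before and after treatment. The proportion with its 95% confidence interval is the stated primary analysis. If it includes patients who started above the threshold, it mixes entry level with drug effect, and two analysts could score the same patient differently. The proportion maintaining the increase inherits the problem.

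The only sample-size statement (sections 8.2.1 and 8.2.2) interprets zero responders among 15. That interpretation presumes that a patient with no drug effect counts as a non-responder.

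**Working it through.** **1. The plan's own figure.** Sections 8.2.1 and 8.2.2 treat 0 of 15 as making a true rate above 20% unlikely. The exact one-sided 95% upper limit is 1 − 0.05^(1/15) = 18.1%. The exact two-sided limit is 1 − 0.025^(1/15) = 21.8%. The rule of three gives 3/15 = 20.0%. The figure reproduces.

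**2. Effect on the primary proportion.** Inputs: 15 treated patients (section 3.1), an inert drug, and h patients entering above 50,000/ul who each have at least one later count above it. The documents give no value for h, so 0 to 3 is assumed. Intervals are Clopper-Pearson.

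| h | Literal rule | 95% CI |
|---|---|---|
| 0 | 0/15 = 0% | 0–21.8% |
| 1 | 1/15 = 6.7% | 0.2–31.9% |
| 2 | 2/15 = 13.3% | 1.7–40.5% |
| 3 | 3/15 = 20.0% | 4.3–48.1% |

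If a rise from at or below 50,000/ul is required and all 15 stay in the denominator, every row becomes 0/15.

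With a working drug, suppose five patients truly cross and h = 2. The literal rule gives 7/15 = 46.7% (21.3–73.4%). Requiring a crossing gives 5/15 = 33.3% (11.8–61.6%). Restricting to low entrants gives 5/13 = 38.5% (13.9–68.4%).

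**3. Would an unchanged high entrant be scored a responder?** Model: independent lognormal counts with mean m and coefficient of variation CV, so σ² = ln(1 + CV²), μ = ln m − σ²/2, p = 1 − Φ((ln 50,000 − μ)/σ), and the chance that any of k counts qualifies is 1 − (1 − p)^k. The documents give no CV, so 10–35% is assumed. The Schedule of Events gives k = 3 (week 2, week 4, month 2), or k = 4 if month 3 falls inside 12 weeks.

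For m = 60,000/ul:

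- CV 10%: p = 0.962; k = 3 gives 1.000.
- CV 20%: p = 0.794; k = 3 gives 1 − 0.206³ = 0.991.
- CV 35%: p = 0.643; k = 3 gives 1 − 0.357³ = 0.954; k = 4 gives 0.984.

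The patient is scored a responder with chance 95–100%. One such patient alone therefore holds the chance of seeing zero responders to at most 1 − 0.954 = 4.6%.

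**4. What a baseline rule leaves unsolved.** Take a stable m = 45,000/ul. At CV 10% and 20%, p = 0.134 and 0.264. Section 6.1 calls for weekly CBCs during dose adjustment, so k = 12 is added.

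| k | CV 10% | CV 20% |
|---|---|---|
| 3 | 35% | 60% |
| 4 | 44% | 71% |
| 12 | 82.3% | 97.5% |

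The section 1.2 doubling criterion was simulated for the same patient (1,000,000 patients, four counts, single Day 1 baseline at or below 50,000/ul). It is met by chance in about 0–3% at CV 10–20%, but 28% at CV 35%.

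**The case against.** A reader might infer that section 8.3.1.1 contradicts itself. The documents do not support that. The working rule opens with a reason about dose changes, so it can fairly be read as setting the time window for the increase already named. On that reading the definition is loose. What stands is that the sentence an analyst would program has no baseline term, and no other section says how a 50,000–75,000/ul entrant is classified.

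The second objection is that few or no such patients will enrol. Section 1.1 describes counts often below 10,000–30,000/ul, and the futility rule in section 4.4.1 (no rise above 30,000 in eight consecutive patients) also presumes low starting counts. This is a fair limit on the size of the problem. It does not remove it, because the ceiling makes such patients eligible and each is one fifteenth of the result.

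Third, the study is exploratory and has no success threshold. Sections 3.1 and 8.3.1.1 already allow within-patient comparison, including an optional Wilcoxon signed-rank test, and by-visit summaries would show that a patient had not changed. All true, but none of these corrects the primary proportion.

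**Conclusion.** The concern holds as a gap in the response definition that should be closed. Taken literally, the rule scores an unchanged entrant at 50,000–75,000/ul as a responder. Each such patient adds up to 6.7 points of 15, and a single one makes the zero-responder reading of section 8.2.1 nearly unobservable. The proportions and intervals are exact for the assumed h. The scoring probabilities rest on the assumed lognormal model and CVs. The harm is to interpretation, not to a formal decision.

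Three stronger conclusions are tempting and not supported:

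- **That the reported rate will be inflated.** There is no baseline distribution, and h may be zero.
- **That averaging Screening and Day 1, or requiring a doubling, settles the matter.** At CV 35%, a stable 60,000/ul patient is placed at or below 50,000/ul in 36% of cases with a single baseline and 33% with the average. Chance doubling at 45,000/ul is 28% and 19%.
- **That section 8.2.1 demands some minimum number of low entrants.** It gives no confidence level. At a true rate of 20%, zero responders has probability 0.8^15 = 3.5%, 0.8^13 = 5.5% or 0.8^12 = 6.9%, and nothing in the text picks a cut-off.

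**What to change.** In section 8.3.1.1:

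1. Define response as a pre-dose Day 1 count at or below 50,000/ul followed by a post-dose count above 50,000/ul within 12 weeks.
2. Keep all treated patients in the denominator. Count those entering above 50,000/ul as not meeting the endpoint, and describe them separately by change from baseline.
3. Report the proportion among patients with baseline at or below 50,000/ul as a supportive analysis.
4. Apply the same baseline rule to the proportion maintaining the increase.
5. Report the section 1.2 criterion as a further supportive analysis.
6. Record that the change was made after preliminary results were known, since section 1.2 already reports five enrolled patients.

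**Cost.** No new visits or samples are needed. The response rate may be slightly lower, because high entrants cannot respond; the supportive proportion shows the effect of that. Entrants just below the threshold can still cross by chance, and more often if weekly counts are used, so the report should say so. The doubling criterion reduces this but does not remove it when counts vary widely.

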8.3.1.2. Safety Analyses

Descriptive statistics will be used to summarize the extent of exposure to eltrombopag.

The number (%) of subjects with Adverse Events and Serious Adverse Events will be reported.

Laboratory parameters will be summarized by visit using descriptive statistics.

9. STUDY CONDUCT CONSIDERATIONS

9.1. Regulatory and Ethical Considerations, Including the Informed Consent Process

Subjects will be given the consent to review prior to requesting their signature so that sufficient time is provided for the subject to consider the study. Risks and benefits will be explained in their entirety to patients. If necessary, an interpreter will be obtained to assist the patient. Any questions that the patient has will be answered prior to signing consent.

The study will be conducted in accordance with International Conference on Harmonization Guidelines for Good Clinical Practice, and the Declaration of Helsinki.

9.2. Quality Control (Study Monitoring)

None needed for investigator-initiated pilot study.

9.3. Quality Assurance

Pharmacy and clinical records.

9.4. Records Retention

7 years.

10. APPENDICES

1. SCHEDULE OF EVENTS ON THE LAST PAGE OF THE PROTOCOL (PAGE 25).

2. WEEKLY DOSE ADJUSTMENT FOR PLATELET COUNTS:

PLATELET COUNT	DOSE ADJUSTMENT
>200 Gi/L	dose reduced by at least 5%
50 to 200 Gi/L	Maintain current dose
<50 Gi/L and/or Significant Bleeding	Increase daily dose by at least 5% up to 75mg daily

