Eltrombopag starting doses for children < 50kg will be scaled by body weight and the starting dose will be approximately 2 mg/kg once daily unless they are of East Asian origin in which case they will use approximately 1 mg/kg as their initial dose. This starting dose is based on the findings of GlaxoSmithKline's PETIT2 study: Eltrombopag for children with chronic immune thrombocytopenia (PETIT2): a randomised, multicentre, placebo-controlled trial.

This dosing schedule is based on those used in GlaxoSmithKline's 'PETIT' study: Eltrombopag in Pediatric patients with Thrombocytopenia from ITP.

For young children unable to swallow a tablet, eltrombopag powder for oral suspension (Eltrombopag PfOS) will be used. Each sachet contains eltrombopag equivalent to 20mg per gm of powder. Please see Appendix 3 for details and dose adjustment guidelines for subjects receiving the suspension formulation. Repeat assessment with the same testing will be performed at week 4. Dose adjustment will be based on the monthly monitoring of the platelet count.

The IPF will be measured at each visit with the CBC. Platelet count data will be collected throughout the study and used as part of the assessment of efficacy. Platelet count data will be collected as part of the CBC monthly during the first year of administration of study drug and at any dose change (eltrombopag or concomitant medication). If a subject continues on a stable dose during any stage of the study for greater than 4 weeks, a CBC (including platelet count) with differential will be performed no less frequently than every 4 weeks. Further information regarding reduction in use of concomitant medications for thrombocytopenia, use of rescue therapy, incidence and severity of bleeding and other symptoms associated with thrombocytopenia and infections will also be collected and summarized.

Platelet function will be assessed by whole blood flow cytometry as described by and in collaboration with [name] (see appendix for attached abstracts).

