5.7. Treatment Plan

	Adults and children > 30 kg	Children < 30 kg	Frequency
Urinalysis	10 mL	5 mL	One Time (at screen)
Admission Panel (includes ALT, AST, bilirubin)	2 mL	2 mL	Every two weeks for the first month; monthly for year 1; every 2 months for year 3; every three months for years 3 - 6
CBC with Platelet and Differential and Immature Platelet Fraction (IPF)	2 mL	2 mL	Every two weeks for the first month; monthly for year 1; every 2 months for year 3; every three months for years 3 - 6
PT/PTT, D-Dimers, Fibrinogen	5 mL	2.5 mL	One time (at screen)
PFA	5 mL	2.5 mL	One time (at month 2)
Single Platelet Flow Cytometry	10 mL	2 mL	3 times (at screen, at month 1-3 and at year 1-2)

NOTE: see schedule of events on page 25

Control subject blood draw	30 mL	10-20 mL	One time
WAS Non-treatment subject blood draw	30mL	10-20mL	One time

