6. STUDY ASSESSMENTS AND PROCEDURES

6.1. Critical Baseline Assessments

Complete Blood Counts (CBCs)

CBCs, including platelet counts and peripheral blood smears, will be monitored prior to initiation, throughout, and following discontinuation of therapy with PROMACTA. Prior to the initiation of PROMACTA, the peripheral blood differential will be examined to establish the extent of red and white blood cell abnormalities. CBCs, including platelet counts and peripheral blood smears, will be obtained weekly during the dose adjustment phase of therapy with PROMACTA and then monthly following establishment of a stable dose of PROMACTA. CBCs, including platelet counts will be obtained weekly to biweekly for at least 4 weeks following discontinuation of PROMACTA.

Liver tests

Serum liver tests (ALT, AST, and bilirubin) will be monitored prior to initiation of PROMACTA, every 2 weeks during the dose adjustment phase and monthly following establishment of a stable dose. If bilirubin is elevated, fractionation will be performed. If abnormal levels are detected, the tests will be repeated within 3 to 5 days. If the abnormalities are confirmed, serum liver tests will be monitored weekly until the abnormality(ies) resolve, stabilize, or return to baseline levels. PROMACTA will be discontinued based on the stopping rules outlined in section 6.3.1

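### Dose-adjustment interval is weekly, two-weekly or monthly depending on the section, and the Schedule of Events omits tests required during dose adjustment

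*Combined protocol and SAP*

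**What the plan says.** **Dose interval.** Three statements stand in the current text.
- Appendix 2 is headed "WEEKLY DOSE ADJUSTMENT FOR PLATELET COUNTS", and the table of contents repeats the heading.
- Section 8.3.1.1 reasons that since the dose "may only be changed every 2 weeks, a platelet count > 50,000/ul at any time within the first 12 weeks" is to be counted as a response.
- Section 3.1 says: "Dose adjustment will be based on the monthly monitoring of the platelet count".

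**Tests during dose adjustment.** Section 6.1 says CBCs and smears "will be obtained weekly during the dose adjustment phase of therapy with PROMACTA and then monthly following establishment of a stable dose of PROMACTA". The same section asks for liver tests "every 2 weeks during the dose adjustment phase and monthly following establishment of a stable dose", and sections 6.3 and 6.3.1 repeat that liver rule.

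**Tests as scheduled.** Section 5.7 gives, for both the CBC and the panel with the liver tests: "Every two weeks for the first month; monthly for year 1". Section 6.2 has: "Collection of platelet counts on week 1 (pre-dose), week 2, monthly during year 1". The Schedule of Events has columns for weeks 2 and 4, then months 2 to 12, and its footnote 4 reads: "Subjects will have their blood drawn monthly and be seen every 3 months during the first year".

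**Dose step.** Appendix 2 sets a minimum increase of 5% and a 75 mg daily cap, with no maximum step. Section 3.1 points all titration to Table 1, but Table 1 covers only the suspension at 8 to 25 kg.

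**The concern.** The three intervals cannot all be routine. A site that adjusts weekly breaks 8.3.1.1, and a site that adjusts monthly does not deliver what the Appendix 2 heading promises. The plan gives no order of precedence and does not define the end of the dose adjustment phase, on which the testing frequency in 6.1 depends.

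Two things are at stake. The first is safety: liver tests drive both the patient withdrawal criteria and a study stopping rule, and a site working from the Schedule would miss some of the required ones while doses may still be rising. The second is the primary endpoint. A single count above 50,000/ul by week 12 is enough, so a patient's chance of being called a responder depends on the dose reached and on how often the count is taken. Both depend on which section the site follows.

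**Working it through.** **The plan's own figure.** Sections 8.2.1 and 8.2.2 say that 0 responders in 15 makes a true rate above 20% unlikely. The rule of three gives 3/15 = 20.0%, and the exact one-sided 95% bound is 1 − 0.05^(1/15) = 18.1%. The figure reproduces and is not in dispute.

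**Dose-change opportunities.** A change made at week 12 cannot affect a response counted by week 12, so only earlier points matter. Month 2 is taken as week 8. The last column is an illustration: a 10 kg child on suspension, with the Table 1 start of 20 mg and step of 6 mg, whose count rises but stays below 50 Gi/L. After k increases the dose is min(75, 20 + 6k).

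| Rule | Change points (weeks) | Most changes, k | Dose by week 12 |
|---|---|---|---|
| Weekly (Appendix 2) | 1 to 11 | 11 | 20 + 66 = 86, capped at 75 mg |
| Every 2 weeks (8.3.1.1) | 2, 4, 6, 8, 10 | 5 | 20 + 30 = 50 mg |
| At each Schedule count | 2, 4, 8 | 3 | 20 + 18 = 38 mg (40 after sachet rounding) |
| Monthly (3.1) | 4, 8 | 2 | 20 + 12 = 32 mg |

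Sachet rounding from the Table 1 footnote is applied only to the dose reached.

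**Post-dose counts by week 12.**
- Schedule and 5.7: weeks 2 and 4, month 2 and month 3. That is 4, or 3 if month 3 falls at week 13.
- Section 6.1: weekly while adjusting, so up to 12 if adjustment lasts the whole window, and fewer once the dose is stable.

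**Gap against the 2-week rule.** That rule needs a decision at weeks 2, 4, 6, 8 and 10. The Schedule supplies counts at 2, 4 and 8, leaving weeks 6 and 10 uncovered. The two-weekly liver panel is missing at the same two weeks.

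**Effect on the response proportion.** One patient reclassified among 15 moves it by 1/15 = 6.7 percentage points. How many would be reclassified cannot be derived. To show why, assume a patient at a fixed dose exceeds 50,000/ul at any one count with probability q, and compare 12 counts with 4:
- Independent counts, 1 − (1 − q)^n: 21.5% against 7.8% at q = 2%, and 71.8% against 34.4% at q = 10%.
- Latent correlation 0.8 between counts (simulated): about 7.7% against 4.7% at q = 2%, and 27.6% against 19.3% at q = 10%.

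The documents give neither q nor the correlation, so these figures show direction only.

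**The case against.** The best defence is that the sections fit together better than they first appear. Section 6.1 is coherent alone: weekly while adjusting, monthly once stable. For anyone still adjusting, its weekly counts cover weeks 6 and 10. Section 3.1 adds a CBC whenever the dose changes and, on a stable dose, sets four-weekly counts as a minimum. The word weekly in Appendix 2 is only a heading, and 8.3.1.1 states the 2-week interval in the same sentence as the response window. The study is an exploratory pilot with descriptive analysis and no hypothesis test on response.

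Much of this stands, and it rules out three stronger readings.
- A reader might infer that the dosing plan cannot be followed at all. It can, by a site that works from 6.1 and 8.3.1.1.
- A reader might treat dose paths such as those in the table as ceilings. They are not. Appendix 2 gives a floor and no maximum, so a 25 mg tablet starter could go to 75 mg at the first change. The suspension steps are initial guidance only. Table 1 starts at 2 mg/kg, already above the 1.5 mg/kg in section 4.4.2, so a patient with no increase at all could be stopped early. The illustration needs a partial rise.
- A reader might infer that the response rate is inflated by a known amount. No such amount can be derived.

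The defence does not remove the gap. Sections 5.7 and 6.2 and the Schedule agree with each other against 6.1, and nothing says that 6.1 prevails. A count triggered by a dose change cannot supply the decision to make that change, except where significant bleeding is the trigger.

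**Conclusion.** The inconsistency is real and worth correcting, but it does not invalidate the study. Three dose intervals coexist, and the weekly CBCs and two-weekly liver tests required during adjustment disappear from 5.7 and the Schedule after week 4. There is no precedence rule and no definition of when adjustment ends.

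Its size can be stated only as opportunities: up to 11, 5, 3 or 2 dose changes before week 12, and 3 to 4 counts against up to 12. These are maxima for a patient who stays below 50 Gi/L, is not stopped, and is still adjusting throughout the window. The spread of 32 to 75 mg for a 10 kg child assumes in addition a constant 6 mg step. The safety consequence needs no such assumptions: a site following the Schedule would omit liver tests that three sections require.

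**What to change.** 1. State one routine interval for dose increases to week 12: every 2 weeks, as 8.3.1.1 already assumes. Allow earlier changes for significant bleeding or a count above 200 Gi/L. Align the Appendix 2 heading and section 3.1.
2. In the Schedule and 5.7, show the weekly CBC and two-weekly liver panel already required during dose adjustment, including weeks 6 and 10 for patients still adjusting. Define the end of adjustment, for example after 4 weeks on an unchanged dose.
3. In 3.1, refer titration to Appendix 2 for tablets and to Table 1 for the suspension only.
4. Keep the primary response definition. Add a sensitivity analysis using only the counts common to all patients (weeks 2, 4, 8 and 12), and list each patient's number of counts and highest dose by week 12. Chances to qualify remain unequal in the primary result; this analysis shows whether that matters.

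**Cost.** Mostly wording. Where the Schedule rather than 6.1 has been followed, a patient who adjusts through week 12 would have up to 12 − 4 = 8 more CBCs of 2 mL (16 mL) and two more 2 mL liver panels, which can share a draw. Patients who stabilise sooner need fewer. The main drawback is that routine increases are slower than under a weekly rule.
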